## 10.3 Method of statistical analysis in relation to objectives

If nothing else is stated, descriptive statistics will be given for each variable in the study and p-values may be complemented by confidence intervals as appropriate.

All p-values presented will be two-sided. A p-value less than 5% will be called “statistically significant” but all conclusions will be based on the primary objective and hence multiplicity is accounted for even though careful interpretations are necessary as multiple tests are performed. No formal adjustment for multiplicity will be applied and nominal p-values will be presented. All confidence interval will be two-sided and 95%.

When calculating p-values a non-parametric statistical approach will be applied because of the nature of the data. Confidence interval will be calculated using distribution assumptions.

The primary objective will be analysed using the exact Binomial test and a parametric confidence interval for the true proportion of implants surviving will be presented

The safety profile will be analysed using descriptive statistics only.

The planned statistical methods for the efficacy evaluation is presented by objective below:

Primary Objective	Corresponding Primary Outcome Variable	Statistical Method
Implant survival	Implant in situ during study	The exact Binomial test and a parametric confidence interval for the true proportion of implants surviving will be presented

Secondary Objective(s)	Corresponding Secondary Outcome Variable(s)	Statistical Method
Implant stability	Stability	A parametric confidence interval for the true proportion of implants with stability = “yes” will be presented
Bone tissue response	Marginal Bone Level (MBL)	The change over time will be tested using the Wilcoxon signed rank test and a parametric confidence interval presented.
Soft tissue response	Plaque, Probing Pocket Depth (PPD) and Bleeding on Probing (BoP)	The change over time will be tested using the Wilcoxon signed rank test and a parametric confidence interval presented.
Patient reported outcomes	OHIP-14	The change over time will be tested using the Wilcoxon signed rank test and a parametric confidence interval presented.

Secondary Objective(s)	Corresponding Secondary Outcome Variable(s)	Statistical Method
Implant success	Implant in situ, no mobility, no pain, no exudates and <2 mm MBL alterations from Implant Placement to 5-year Follow-up visit	A parametric confidence interval for the true proportion of implants with success = "yes" will be presented
Prosthetic survival	Original restoration in place	A parametric confidence interval for the true proportion of restorations in place = "yes" will be presented
Prosthetic success	No need of technical repair	A parametric confidence interval for the true proportion of restorations with need of technical repair = "no" will be presented
Avoidance of augmentations	Proportion of augmentations avoided by using six 6.6 mm implants instead of six 8.0 mm implants (SIMPLANT®)	A parametric confidence interval for the true proportion of augmentations when using six 8.0 mm implants but not when using six 6.6 mm implants.

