### 2.2 Secondary objectives

Secondary Objective(s)	Corresponding Secondary Outcome Variable(s)
Implant stability	Stability
Bone tissue response	Marginal Bone Level (MBL)
Soft tissue response	Plaque, Probing Pocket Depth (PPD) and Bleeding on Probing (BoP)
Patient reported outcomes	OHIP-14
Implant success	Implant in situ, no mobility, no pain, no exudates and <2 mm MBL alterations from Implant Placement to 5-year Follow-up visit
Prosthetic survival	Original restoration in place
Prosthetic success	No need of technical repair
Avoidance of augmentations	Number of sites (pre-defined) virtually suitable for 6.6 mm long v.s. 8.0 mm long implants (SIMPLANT®)

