#### 6.3.2 Secondary outcome variables

##### 6.3.2.1 Secondary outcome variable(s)

- Implant stability
- Marginal Bone Level alterations
- Soft tissue response (Plaque, PPD, BoP)
- OHIP-14
- Implant success
- Prosthetic survival
- Prosthetic success
- Number of avoided augmentations

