OHIP-14 includes seven domains and is therefore able to cover a wide range of possible oral health problems that may have an impact on quality of life. The domains are: functional limitation, pain, psychological discomfort, physical disability, psychological disability, social disability and handicap. OHIP attempts to measure both the frequency and severity of oral problems on functional and psychosocial well-being. An example of an OHIP statement is "Have you had to interrupt meals because of problems with your teeth, mouth or dentures". Responses are based on a Likert scale (i.e., 0 = never, 1 = hardly ever, 2 = occasionally, 3 = fairly often, 4 = very often).

- ***Implant success***

Implant success will be evaluated as defined by the ICOI Pisa Consensus Conference 2008 [35]. An implant will be considered successful if all of the following criteria are fulfilled:

- Implant still in place
- No mobility
- No pain or tenderness upon function
- <2 mm marginal bone loss from initial surgery to 5-year follow-up visit
- No history of exudates

- ***Prosthetic survival***

A prosthetic restoration will be considered a *survivor* if the original restoration is still in place at the follow-up visit, regardless of its condition.

- ***Prosthetic success***

A prosthetic restoration will be considered as successful if it has remained unchanged and there has been no need of technical repair during the observation period.

The occurrence of any technical repair of the prosthesis or any biological complications related to the prosthesis will be registered and reported as ADEs (section 6.4.1.2).

- ***Number of avoided augmentations***

The proportion of augmentations avoided by using six 6.6 mm implants instead of six 8.0 mm implants will be virtually evaluated by using the SIMPLANT file generated from the CBCT at Visit 2. First, six regions of interest will be defined in SIMPLANT by indicating the mesial and distal borders of the canine, premolar and molar regions on both left and right side. An evaluator, independent from the investigational group and DENTSPLY Implants, will then make a surgical planning with six 6.6 mm implants placed at the pre-defined canine, premolar and molar regions and count the number of sites that would need augmentation. The evaluator will then repeat this

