procedure but now use six 8.0 mm implants for the planning. If necessary, the evaluator will be allowed to exceed the region borders slightly when doing the surgical planning, in order to achieve maximal bone amount (to reflect the real situation).

The difference in number of needed augmentations for the 8.0 mm implants and the 6.6 mm implants divided by the number of needed augmentations for the 8.0 mm implants will represent the proportion of augmentations avoided by using the 6.6 mm implant.

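### The interval planned in 10.3 for avoided augmentations is not tied to the net ratio defined in 6.3.2.2, and its denominator is not stated

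*Combined protocol and SAP*

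**What the plan says.** Section 6.3.2.2 (Number of avoided augmentations) has one independent evaluator plan six 6.6 mm implants on the Visit 2 SIMPLANT file and "count the number of sites that would need augmentation". The evaluator then repeats the exercise with six 8.0 mm implants. In either plan, if necessary, "the evaluator will be allowed to exceed the region borders slightly when doing the surgical planning". The estimate is then defined: "The difference in number of needed augmentations for the 8.0 mm implants and the 6.6 mm implants divided by the number of needed augmentations" at 8.0 mm.

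In the table of 10.3, the outcome column names the proportion of augmentations avoided, in line with 6.3.2.2. The method column beside it promises a parametric confidence interval for the "true proportion of augmentations when using six 8.0 mm implants but not when using six 6.6 mm implants". It gives no denominator and does not refer back to the formula.

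Section 2.2 lists the outcome as "Number of sites (pre-defined) virtually suitable for 6.6 mm long v.s. 8.0 mm long implants", and 6.3.2.1 labels it "Number of avoided augmentations". No section says whether the proportion is pooled over sites or calculated per subject. Section 10.3 makes all intervals two-sided at 95%, and 10.4 treats implants as independent units.

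**The concern.** The estimate in 6.3.2.2 subtracts one total from another. The target of the interval in 10.3 is a single group of sites: those scored as needing augmentation at 8.0 mm and not at 6.6 mm. Sites scored the other way round reduce the first quantity and leave the numerator of the second unchanged. The base of the second could be the 8.0 mm augmentations or all planned sites. An analyst who follows both sections literally could print a point estimate and an interval that belong to different quantities.

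This is a secondary outcome without a test, and 10.3 rests all conclusions on the primary objective. But 1.2 names avoided augmentations as the further interest of the study, and 7.8 and 10.5 plan a separate publication from the Visit 2 data, before the clinical follow-up results. If the definition stays open until then, it can be chosen with the results in view.

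**Working it through.** **Inputs.** The definitions are those of 2.2, 6.3.2.2 and 10.3. The documents state no rate or expected value for this outcome, so there is no planned figure to reproduce. For scale, 56 subjects (10.4) × 6 sites = 336 sites. All cell counts and rates below are assumptions.

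**Step 1: put the definitions on one table.** Classify each site by its two scores: a = augmentation needed at both lengths, b = at 8.0 mm only, c = at 6.6 mm only, d = at neither; N = a + b + c + d.

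- 2.2, reading suitable as needing no augmentation: b + d sites for 6.6 mm against c + d for 8.0 mm; the difference is b − c.
- 6.3.2.2: [(a + b) − (a + c)]/(a + b) = (b − c)/(a + b).
- 10.3 method column: b/(a + b) or b/N, depending on the unstated denominator.

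**Step 2: when do they agree?** With the 8.0 mm augmentations as base, the 10.3 quantity minus the 6.3.2.2 ratio is c/(a + b), which is zero if c = 0 and positive otherwise. With all sites as base, the 10.3 quantity exceeds the ratio only if c > b[1 − (a + b)/N]. For a = 40, b = 80, N = 336 this is c > 80 × (1 − 120/336) = 51.4. Below that it is lower.

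**Step 3: illustrative counts, N = 336.**

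| a | b | c | 6.3.2.2: (b−c)/(a+b) | 10.3: b/(a+b) | 10.3: b/N |
|---|---|---|---|---|---|
| 40 | 80 | 0 | 66.7% | 66.7% | 23.8% |
| 40 | 80 | 4 | 63.3% | 66.7% | 23.8% |
| 40 | 80 | 10 | 58.3% | 66.7% | 23.8% |
| 40 | 80 | 20 | 50.0% | 66.7% | 23.8% |
| 100 | 180 | 5 | 62.5% | 64.3% | 53.6% |
| 30 | 10 | 20 | −25.0% | 25.0% | 3.0% |

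The last row is extreme, but it shows that the net ratio can be negative. An interval built for a binomial proportion cannot represent that.

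**Step 4: how c could arise.** Assume true need of 40% at 8.0 mm and 15% at 6.6 mm, nested, and let each reading be wrong independently with probability e. The scored need is q = p(1 − e) + (1 − p)e. At e = 5%, q8.0 = 0.41 and q6.6 = 0.185, so the net ratio is 0.225/0.41 = 54.9%. The 8.0 mm-only share is 0.15(0.05)(0.95) + 0.25(0.95²) + 0.60(0.05)(0.95) = 0.26125, so b/(a + b) = 0.26125/0.41 = 63.7%.

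| e | Net ratio | b/(a+b) | Gap (points) |
|---|---|---|---|
| 0 | 62.5% | 62.5% | 0 |
| 2% | 59.4% | 63.1% | 3.7 |
| 5% | 54.9% | 63.7% | 8.8 |
| 10% | 47.6% | 64.3% | 16.7 |

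At e = 0 the all-site version is 0.40 − 0.15 = 25.0%, against 62.5% for the net ratio. If length made no difference (need 40% at both) and e = 5%, the net ratio would be 0 and b/(a + b) would be 0.0475/0.41 = 11.6%.

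**Step 5: fit of the interval.** With c = 0 the ratio is b/(a + b), a share of the 8.0 mm augmentations. With c > 0 it is not a binomial proportion. In both cases the denominator is itself a random total, and the sites come six to a jaw. A per-subject version would be undefined for any subject with no augmentation needed at 8.0 mm, so the level of pooling has to be stated.

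**The case against.** The strongest reply is that these are loose wordings of one idea. Much of it stands.

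- The outcome column of 10.3 agrees with 6.3.2.2, and the difference between the two counts in 2.2 is the numerator of the 6.3.2.2 ratio. A reader might infer three rival definitions, but the documents do not support that. The conflict lies in the method column of 10.3.
- Bone that takes an 8.0 mm implant would normally take a 6.6 mm one at the same spot, so c should be near zero. The allowance to cross borders serves to find the most bone in both plans. This stands as an expectation. But nothing requires the same position in both plans or forbids a site scored as needing augmentation at 6.6 mm alone.
- The independent-error model is an assumption. One evaluator reads one file twice in sequence and could carry the same misreading into both plans. If so, c = 0 and the gap disappears whatever the error rate. For that reason the gaps in step 4 are illustrative and their range starts at zero.
- The method column speaks of a proportion of augmentations, which, read with 6.3.2.2, suggests the 8.0 mm augmentations as base. That is the more natural reading, but it is not stated; site counts in 2.2 and implants as units in 10.4 leave all sites open.
- Clustering within jaws is a wider matter than this outcome. That is true, but any replacement interval has to take a position on it.

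**Conclusion.** The mismatch is real: the plan defines one quantity and attaches its interval to another whose denominator is not given. The two coincide only with the 8.0 mm augmentations as base and no 6.6 mm-only site.

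A reader might infer that 10.3 moves the interval to a systematically more favourable quantity. The documents do not support this. It needs both the 8.0 mm base and some 6.6 mm-only sites, and they establish neither. With the 8.0 mm base and c = 0 the gap is zero. With that base and c > 0 the 10.3 figure is higher, by c/(a + b). With all sites as base it is usually lower, for example 25.0% against 62.5%.

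The size in this trial cannot be given, because the documents contain no augmentation rates, reading-error rates or agreement data. The point is one of clarification for a secondary outcome. It deserves settling because a separate publication depends on it.

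**What to change.** 1. In the method column of 10.3, name the 6.3.2.2 net ratio, (N8.0 − N6.6)/N8.0, pooled over all subjects, as the quantity estimated. Refer to the same formula in 2.2.
2. Replace the parametric interval for a proportion with a two-sided 95% interval for this ratio that treats the subject as the sampling unit, for example a bootstrap that resamples subjects.
3. Report the paired 2×2 site table (needed at both lengths, 8.0 mm only, 6.6 mm only, neither) beside the ratio, so that readers can see whether any site went the other way and can derive the per-site figure.
4. Settle this before the Visit 2 partial clean file in 10.5.

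The cost is a few lines of text and of analysis code. No new assessment is needed, provided that the evaluator's scores are kept by site. Section 6.3.2.2 speaks only of counting sites, so this should be confirmed: totals per jaw would be enough for the ratio but not for the paired table. If some sites are 6.6 mm-only, the reported percentage will be lower than a one-directional figure on the 8.0 mm base.

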#### 10.4 Determination of sample size

In this study each subject will get 6 implants. However, in the statistical analysis the implants will be assumed to be independent and therefore used as the statistical unit.

Clinical studies with follow-up periods of 1-17 years report survival rates ranging between 93 and 100% for ANKYLOS implants  $\geq$  8 mm [36-39]. A recently completed study on implant treatment of the edentulous maxilla with the ASTRA TECH Implant system (length 8-17 mm) reported a survival rate of 93% after 5 years (data not yet published). There is no indication that the survival rate for the ANKYLOS 6.6 mm implant would differ from the longer ANKYLOS implants and due to the similarity with the ASTRA TECH study mentioned above, the true five-year survival rate for the 6.6 mm ANKYLOS implant is assumed to be 93%-95%.

The aim of the study is to show that the implant survival rate is not less than  $\pi_1$ . This means that the null-hypothesis  $H_0: \pi < \pi_1$  will be tested and if rejected (i.e. the one-sided p-value is less than 0.0250) the alternative hypothesis, i.e.  $H_1: \pi \geq \pi_1$ , will be accepted. The test to be used is the exact Binomial test.

As the assumed implant failure rates are close to 0 it cannot be assumed normal approximation is valid and hence exact methods for sample size determination is applied by means of StatXact (version 10.1).

In Table 1, the total number of implants needed in order to reach 80% and 90% power to reject the null-hypothesis is given when assuming true implant survival rates between 93% and 95%.

**Table 1** Number of needed implants in order to test the null hypothesis that the survival rate is at least  $\pi_1$  by power 80% and 90% and by true survival rate between 93% and 95%. The number of subjects is given by dividing the number of implants by 6. (by StatXact, version 10.1)

Power	$\pi_1$	True survival rate ( $\pi$ )		
		0.93	0.94	0.95
80%	0.85	135	102	75
	0.88	292	191	139
	0.90	719	398	242
90%	0.85	176	135	102
	0.88	380	252	180
	0.90	942	503	304

As seen in Table 1, a total of 304 implants will be needed in order to reach 90% power to reject the null-hypothesis that the survival rate is less than 90% if the true implant survival rate is 95%. Since each subject will receive 6 implants, this means that a total of  $304/6=51$  fully evaluable subjects will be required.

In this subject population we expect a 10% drop-out rate from the study over a 5-year period. In order to ensure 51 evaluable subjects, 56 subjects will receive implants in the study.

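### The primary binomial test treats six implants in one jaw as independent, so its one-sided 2.5% error rate is not protected against within-subject correlation

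*Combined protocol and SAP*

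**What the plan says.** Section 10.4 notes that every subject receives six implants and then sets the clustering aside: "in the statistical analysis the implants will be assumed to be independent and therefore used as the statistical unit". It gives no reason. Section 10.3 follows suit: "The primary objective will be analysed using the exact Binomial test", applied to the proportion of implants surviving. Rejection requires that "the one-sided p-value is less than 0.0250". The size of the trial comes from the same calculation: "a total of 304 implants will be needed in order to reach 90% power to reject the null-hypothesis" of survival below 90% when true survival is 95%. Dividing by six gives 51 subjects, and with 10% drop-out "In order to ensure 51 evaluable subjects, 56 subjects will receive implants in the study".

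For intervals, section 10.3 says only that "Confidence interval will be calculated using distribution assumptions". Two secondary analyses are also at implant level: "A parametric confidence interval for the true proportion of implants with stability" and "A parametric confidence interval for the true proportion of implants with success".

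Section 6.3.1.1 adds a subject-level summary, the share of subjects who keep every implant, but attaches no threshold or test to it. Neither document section gives an ICC, a design effect, a robust variance or a model with a subject term.

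**The concern.** The six implants share a host, a jaw and an operation (section 5.1.3), and from Visit 8 they share one full-arch bridge (section 5.1.8). The plan itself treats some determinants of osseointegration as properties of the subject (exclusion criterion 9). It also provides for a subject losing all six implants (sections 5.5.1 and 5.5.3). Under independence at 90% survival the chance of that is 0.10^6, or 1 in a million per subject. None of this proves correlation or gives its size, but it does mean that an ICC of exactly zero needs support.

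Positive correlation makes the failure count more variable than the binomial allows. The count then falls at or below the cut-off too often when true survival is only 90%, so the error runs in favour of the device. Section 10.3 ties all conclusions to the primary objective, so the main claim of the study is exposed.

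**Working it through.** **Inputs.** From section 10.4: six implants per subject, null survival 0.90, true survival 0.95, one-sided level 0.025, 304 implants, 51 evaluable and 56 treated subjects. The documents give no ICC (ρ), so values from 0 to 0.30 are assumed.

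**Step 1: reproduce the plan.** With n implants, reject when failures ≤ c, where c is the largest integer with P(X ≤ c | n, 0.10) < 0.025.

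| Implants | c | Size at 90% survival | Power at 95% survival |
|---|---|---|---|
| 304 (plan) | 20 | 0.0243 | 0.914 |
| 306 (51 × 6) | 20 | 0.0223 | 0.909 |
| 336 (56 × 6) | 22 | 0.0175 | 0.919 |

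The plan's 304 implants for 90% power is consistent with this.

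**Step 2: keep the rule and add correlation.** Let p be the failure probability. Two models for a subject's failures out of six were used:

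- Beta-binomial, with parameters p(1−ρ)/ρ and (1−p)(1−ρ)/ρ.
- All-or-none mixture: with probability ρ all six implants share one outcome; otherwise they are independent.

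Under both, the variance of the count is inflated by 1 + 5ρ. The total over subjects was obtained by exact convolution and compared with c. Ranges cover the two models.

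| ICC | Type I error, 51 | Power, 51 | Type I error, 56 | Power, 56 |
|---|---|---|---|---|
| 0 | 2.2% | 90.9% | 1.8% | 91.9% |
| 0.01 | 2.4-2.5% | 90.4% | 1.9-2.0% | 91.3% |
| 0.05 | 3.2-3.6% | 88.5-88.6% | 2.6-2.9% | 89.5% |
| 0.10 | 4.5-5.0% | 86.5-86.7% | 3.7-4.2% | 87.5-87.6% |
| 0.20 | 7.3-7.9% | 83.5-83.7% | 6.3-6.9% | 84.4-84.5% |

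The type I error crosses 2.5% at ICC 0.010 (beta-binomial) or 0.014 (mixture) with 51 subjects, and at 0.033 or 0.044 with 56. Below those values, the level left unused by the discrete test absorbs the correlation.

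**Step 3: power if 2.5% is held.** The best case is a failure-count test that spends exactly 2.5% with the ICC known. Its power at 95% survival is:

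| ICC | 51 subjects | 56 subjects |
|---|---|---|
| 0.02 | 88.8-89.5% | 91.6-91.9% |
| 0.05 | 84.7-86.0% | 87.8-89.0% |
| 0.10 | 77.7-80.5% | 81.5-83.9% |

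The stated 90% is therefore missed from an ICC of about 0.02 (51 subjects) or 0.05 (56). The shortfall is slight at first and grows with the ICC.

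**Step 4: confidence interval.** The plan does not name its interval, so two were assumed, at 95% survival with 51 subjects. Clopper-Pearson covers 96.6% at ICC 0, 94.2-94.3% at 0.05, 91.7-92.1% at 0.10 and 86.7-87.7% at 0.20; it drops below 95% only from an ICC of about 0.04. Wald covers 93.2% already at ICC 0 and 86.8-87.3% at 0.10.

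**The case against.** The strongest reply is that the ICC is unknown and the harm may be small. With 56 subjects and ICC 0.05 the error is 2.6-2.9% against 2.5%, and errors of 6-8% need an ICC near 0.20, which nothing in the documents supports. This stands as a limit on the size of the problem. It does not justify fixing the ICC at zero when a method can estimate the clustering from the data.

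The two crossing points also depend on discreteness. They alternate with the number of subjects: 0.035-0.047 at 50, 0.010-0.014 at 51 and again at 55, and 0.033-0.044 at 56. Ten per cent drop-out from 56 leaves 56 × 0.9 = 50.4 subjects, and the analysis set in section 10.2 is not defined by completion, so the more tolerant values may apply. That is correct. The figures belong to the subject numbers that the plan names and are not a general tolerance of the design.

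The indirect evidence is weak as well. Excluding subjects with shared risk factors may reduce heterogeneity, a rule for losing all implants may be purely administrative, and the bridge cannot affect losses before about week 17. Section 10.1.2 judges that no covariates matter, which is compatible with independence. These points are fair, but the conclusion does not depend on that evidence. It depends on an unsupported assumption behind the only confirmatory test.

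Finally, the subject-level percentage does not need independence within subjects. Without a threshold or test, however, it cannot carry the claim.

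**Conclusion.** The concern holds, and the analysis must be changed. As written, the primary test keeps its 2.5% level only if the ICC is below about 0.010-0.014 (51 subjects) or 0.033-0.044 (56), and the plan offers no basis for either. At ICC 0.10 the error is about twice the stated level with 51 subjects. The implant-level intervals for stability and implant success rest on the same assumption.

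That the adjustment is missing is certain. The size of the effect is not, because it rests on assumed ICCs, two correlation models, six evaluable implants per subject and the 90% threshold used to size the trial.

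**What to change.** **Section 10.3.** Keep the implant-level estimate and the 90% threshold, and base the primary test and 95% interval on one pre-specified subject-clustered method. One suitable choice is Clopper-Pearson limits on effective counts:

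- With m subjects, N implants, y_i failures among n_i implants in subject i, and p̂ the overall failure proportion, take V_cluster = [m/(m−1)] Σ(y_i − n_i p̂)² / N² and V_binomial = p̂(1−p̂)/N.
- Divide implants and failures by max(1, V_cluster/V_binomial) × (t/z)², with t on m−1 degrees of freedom. Set the max term to 1 if there are no failures.
- Claim success only if the lower limit for survival exceeds 90%.

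A cluster-robust logit interval with t on m−1 degrees of freedom, and a pre-stated fallback for few failures, is an alternative. Use the same clustering for the stability and implant-success intervals. State that the method is approximate, and check it under more than one correlation model before fixing it.

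**Section 10.4.** Delete the independence sentence and restate power at the planned size over an ICC range, for example 0.01-0.20.

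**Cost.** The change needs SAP wording and a different variance estimator, with no new data or enrolment. The loss of power must be disclosed. For the suggested interval at 95% survival (simulated):

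| ICC | Power, 51 subjects | Power, 56 subjects |
|---|---|---|
| 0 | 85% | 90% |
| 0.05 | 77-78% | 81-82% |
| 0.10 | 69-72% | 73% |

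The six-point loss at ICC 0 with 51 subjects (91% to 85%) comes from the method itself. The logit alternative keeps about 88.5% there.

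Nor is 2.5% guaranteed. With 51 subjects the type I error of the suggested interval at ICC 0.05 / 0.10 / 0.20 is 1.8 / 2.2 / 2.7% under the beta-binomial and 1.8 / 2.6 / 4.4% under the mixture. The planned test has 3.2 / 4.5 / 7.3% under that mixture. The logit alternative gives 2.3 / 2.5 / 2.8% and 2.8 / 3.6 / 5.3%.
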